### **4.2 Secondary Objectives**

- a. Test the underlying role of HAB as a mechanism linking HBMT to changes in anger and aggressive behavior.

## **5 HYPOTHESES**

### **5.1 Primary Hypotheses**

- a. Hypothesis 1: Relative to volunteers in the fake-training condition, those volunteers who receive the real HBMT at time-point one will report less state anger and aggression at time-point two.
- b. Hypothesis 2: Effects of HBMT on state anger and aggression in daily life will be mediated by between group differences in HAB.

### **5.2 Secondary Hypothesis**

- a. The effects of HBMT on anger and aggression will diminish over time. In other words, larger effects of HBMT will be observed for volunteers returning sooner (vs later) after time-point one.
- b. We anticipate the most robust impact of HBMT on anger and aggression on high versus low stress days (per self-report).

## **6 BACKGROUND AND MILITARY RELEVANCE**

### **6.1 General Background**

Aggression refers to causing harm to someone who is motivated to avoid that harm (Anderson & Bushman, 2002). Reactive or counter-aggression refers to aggression that results from being provoked or threatened as opposed to unprovoked aggression perpetrated for utilitarian goals (Dodge & Coie, 1987). However, provocations do not always result in reactive aggression. Indeed, the psychological literature is replete with examples of variables that moderate reactive aggression (See Anderson & Bushman, 2002). One key moderator is the extent to which the victim believes that the provocateur acted in an intentionally hostile manner (e.g., being shoved on purpose) versus not intending to be hostile (e.g., being shoved by mistake; De Castro, Veerman, Koops, Bosch, & Monshouwer, 2002). Hostile attributional bias (HAB) is the tendency to attribute hostile intentions to the actions of others when contextual cues are ambiguous (Milich & Dodge, 1984). Elevated HAB is observed in both reactive aggressors and premeditated aggressors. Individual differences such as trait hostility (e.g., Wingrove and Bond,

2005; Wilkowski et al., 2007) and gender (e.g., Matheson et al., 2011) are also correlated with HAB.

There are many reasons why people may attribute hostile intentions to the ambiguous actions of others. For instance, HAB is predicted by situational factors. These include exposure to real or imagine violence, such as violent video games or music (Anderson et al., 2003; Bartlett et al., 2009), social exclusion (DeWall et al., 2009), intoxication (See Osgood and Muraven, 2018), or even exposure to alcohol related information (Subra et al., 2010). Furthermore, developmental factors such as rejection from peers in childhood (Coie and Dodge, 1988) and harsh parenting (Weiss, Dodge, Bates, and Pettit, 1992), can predispose strong HAB.

In general, HAB is more likely to occur in individuals and situations where non-hostile interpretations are less salient than hostile interpretations. Indeed, differences in the cognitive accessibility of hostile vs. non-hostile concepts is an important predictor of HAB and aggression. For example, research participants who complete ambiguous word fragments to form hostile-themed words, tend to attribute more blame and react more aggressively to provocations from confederates (e.g., Bartlett et al., 2009). Further, cognitive priming tasks have successfully moderated blame attributions of negative events (Meier and Robinson, 2004; Graham and Hudley, 1994). Indeed, even priming conceptually related ideas such as hot vs. cold temperature can moderate the likelihood of HAB (DeWall and Bushman, 2009). In a similar vein, manipulations that disrupt higher-order cognitive functions (e.g., cognitive load) can lead to heightened aggression in response to provocations (Osgood and Muraven, 2016).

The psychological literature provides several reasons hostile attributions are often more salient than non-hostile attributions. First, contextual cues related to the harm incurred as a result of a provocation are *often* more salient than cues related to mitigating factors (Finkel et al., 2012; Giancola et al., 2009). For example, suppose an individual cuts others in line at a checkout counter. The offense and the resultant inconvenience to others is obvious, whereas possible mitigating factors (e.g., a store employee may have told the person to cut the line) are often less noticeable. This perception bias is more likely when attention is restricted (Osgood & Muraven, 2017). Second, general attributional biases, such as the fundamental attribution error (Ross, 1977) often operate by overemphasizing the role that an individual's intentions played in their behavior and underestimating the influence of situational factors. This issue is compounded when an individual makes attributions quickly as the less accessible non-hostile concepts may take more time to surface and affect cognition.

HAB is an automatic process that requires slow and effortful controlled processing to override (Gilbert & Malone, 1995; Carlston & Skowronski, 1994, 1995; Winter & Uleman, 1984; Wilkowski, Robinson, & Troop-Gordon 2010). In other words, following provocation, a person's immediate appraisal of the situation is typically hostile, with less hostile considerations taking more time to surface.

To increase the likelihood that ambiguous provocations will be interpreted as non-hostile, people must inhibit making attributions or responding with aggressive behaviors until enough time has passed to consider non-hostile explanations for the provocation. For example, Finkel, DeWall, Slotter, Oaten, and Foshee (2009) found that participants responded more aggressively to their partner's hypothetical infidelity if forced to respond immediately than if made to wait 10

seconds. Similarly, Osgood and Muraven (2016) reduced aggression in provoked research volunteers by imposing extra time to think about reasons to inhibit aggression. Training programs that emphasize increasing the accessibility of non-hostile concepts in the face of ambiguously hostile information and reinforce inhibiting rapid hostile attributions may reduce HAB. Indeed, Hawkins and Cogle (2013) demonstrated a computer-based HAB training that involved repeated exposure to either hostile or non-hostile explanations for a series of hypothetical provocations reduced HAB and aggressive behavior.

*Hostile Bias Modification Training* (HBMT) is a new computer task training for reducing HAB developed by scientists at WRAIR and ARL. The training is based on the Go/No-Go task (Fillmore et al., 2006) and Lexical Decision Task (Lepore and Brown, 2002). The training is theorized to reduce bias by affecting two key factors that drive HAB: relative cognitive accessibility of hostile concepts and rapid attribution-making/aggressive responding in response to ambiguously hostile cues. The training is designed to prime trainees to interpret ambiguous information as non-hostile (by increasing the saliency of non-hostile concepts) and to behaviorally commit to that interpretation quickly. Further, the training is designed to condition the individual to inhibit responding to hostile interpretations before reconsidering the possibility the information may be non-hostile. Relatedly, the training conditions the individual to inhibit responding (behaviorally) to hostile cues. Thus, the training is thought to induce a non-hostile attribution bias while simultaneously training the inhibition behavior in response to provoking cues. In a recent study (WRAIR #2574), online volunteers who completed one session of real HBMT displayed significantly less HAB when asked to interpret the motives of characters in hypothetical vignettes than volunteers who completed a fake version of the training. Although WRAIR #2574 demonstrated HBMT can affect HAB and anticipated behaviors in hypothetical situations, it did not assess real behaviors. Therefore, it is still unclear if and how HBMT is able to affect actual behaviors and anger in real life. The present study would answer this question.

## 6.2 Military Relevance

Hypersensitivity to ambiguous threats, hostile bias, and the resultant inappropriate application of aggression are documented problems that reduce force readiness (Wilk et al., 2015), particularly following combat deployments. This research will continue to test a platform that could be developed into a tool for Soldiers to alleviate hypersensitivity to perceived threats following combat deployments. Further, if this experiment is successful, it would justify future efforts to test this training in a mobile platform that could be used by operational forces in far forward environments where traditional behavioral health care is inaccessible. Under the Military Operational Medicine Research Program (MOMRP) Task Area W1A (Real-time Assessment and Intervention Development), the U.S. Army Medical Research and Materiel Command (USAMRMC) is conducting research addressing the potential utility of computerized cognitive processing optimization tools designed to enhance resilience and mitigate psychological injury. The results of this protocol will produce empirical evidence concerning the efficacy of HBMT for reducing anger and aggression in life. Approval of MOMRP (RAD III) core funding for this project was the result of a vetting process that requires explicit consideration of military relevance.

## 7 STUDY DESIGN

### 7.1 Overview and Duration of Volunteer Participation

In the present study, we propose to examine the effectiveness of HBMT on reducing anger and aggression in up to 400 volunteers (200 completers) divided into two experimental conditions ( $n = 100$  completers in each group). The duration of participation for each volunteer is approximately 60 minutes total across both time-points (see Section 7.8 for procedure breakdown with estimated times).

### 7.2 Determination of Sample Size

200 volunteers (100 completers per condition) are needed to achieve statistical power of 80% and equal groups. The previous (and only other) study to test HBMT found a large effect of the real (vs. placebo) training on HAB ( $d = .78$ ), when HAB was assessed immediately after HBMT. However effect sizes are expected to be smaller in the present study as actual behavior is being assessed and there is a greater time delay (24-96 hours) between HBMT and the behavioral assessment. We will divide this effect size approximately in half ( $d = .4$ ) in our prediction for the second study. Given this effect size, a minimum of 200 completers who follow all task instructions will be needed to achieve 80% power.

### 7.3 Population to be Studied

The target population for this study is adult male and female volunteers from the general population.

## 8 METHODS

### 8.1 Pre-Study Procedures: Advertisements and Recruitment of Volunteers

Adult volunteers meeting eligibility (see Section 8.4) will be recruited by non-coercive means according to applicable US Army Regulations (ARs). Volunteers will be recruited via postings listed on Amazon.com Mechanical Turk (MTurk). MTurk allows researchers to use Amazon.com to recruit participants for online experiments in exchange for a small fee and payment to each participant for their time. This form of recruitment offers several advantages. Namely, it allows for a sample that is relatively more representative of the general (internet using) population than local convenience samples, substantially faster data collection, and larger sample sizes. Several recent empirical analyses of the strengths and weaknesses of MTurk samples have concluded that MTurk samples are of comparable or better quality than undergraduate subject pools (the most common source of volunteers in psychology research; Paolacci & Chandler, 2014). Researchers have determined that MTurk samples are also more representative of the national-population than local convenience samples (Berinsky, Huber, & Lenz, 2012). Furthermore, research testing classic psychological effects using MTurk versus undergraduate students on the same experiments report equivalent results (Goodman, Cryder, & Cheema, 2013). These reports recommend using MTurk for computer experiments where minimal experimenter involvement is needed. Consequently, MTurk has become a popular methodology for collecting data in social-science studies, with over 700 recent articles using

MTurk for participant recruitment (Berinsky, Huber, & Lenz, 2012). Of special relevance to the present research, MTurk volunteers have been used in recent research by US Army research laboratories and US Army research scientists (e.g., Asher et al., 2017; Onal et al., 2014; Rajivan et al., 2016; Roy et al., 2017). HBMT was specifically tested using an MTurk sample previously (WRAIR #2574) with large effect sizes observed.

## **8.2 Study Location**

Volunteers will complete the study via their own internet-connected personal computers. All data will be collected by AI's at ARL utilizing the Volunteerscience.com platform, which is fully integrate-able with MTurk. Volunteerscience.com staff may provide technical assistance with programming the computer tasks designed by the study PI and AI's. Prospective participants will click a link on MTurk, which will redirect them to the experiment web-page hosted by volunteerscience.com. Data is collected and stored by volunteerscience.com.

Volunteerscience.com will transfer data files to AI's/study staff who will transfer data to the PI. Volunteerscience.com will maintain copies of data until the PI confirms receipt of data from Volunteerscience.com. MTurk will not receive any experimental data. The study files and data will be on Federal Risk and Authorization Management Program (FedRAMP) and Defense Information Systems Agency (DISA) authorized servers managed by Amazon Web Services. See section 11.2 for details on information assurance (IA) and operational security (OPSEC).

## **8.3 Study Briefing and Informed Consent**

Volunteers will be presented with an electronic version of the Informed Consent Document (ICD; Appendix C) on the study webpage at the start of each time-point of the study. The ICD provides potential volunteers with information pertaining to study procedures, risks, and benefits related to participation in the study. Volunteers will not be asked to add a signature or any personally identifiable information (PII) to the ICD. However, volunteers will be asked to click a box indicating that they have read and understood the ICD, and agree to participate. If a volunteer clicks that they "do not agree" to participate, they will be redirected to a screen that thanks them for their time and ends the study session.

## **8.4 Volunteer Eligibility**

### **8.4.1 Determination of Eligibility**

MTurk requires that all users are at least 18 years old to create an MTurk account. Prerequisites will be set to restrict participation to MTurk users who are located in the United States and/or other primarily English speaking countries.

### **8.4.2 Inclusion Criteria**

All volunteers must meet the following criteria to be included in the study:

- a. Adult aged 18 and older
- b. Located in the United States or other primarily English speaking country. MTurk allows requestors to limit the ability to view a posting to only those within certain geographical regions.

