The study would utilize up to 400 volunteers (200 completers) recruited via an online commercial recruitment platform to participate in an online study. Volunteers will be asked to participate at two time-points. At time-point one, volunteers would be randomly assigned to complete one of two versions of HBMT. One version is designed to train the brain (rehearse and reinforce) to seek positive interpretations of ambiguous social cues and to inhibit thoughts and behaviors related to hostility. The second is a placebo version that is not expected to affect attitudes, cognitions, or behaviors. These versions were validated in a prior study (WRAIR #2574). Volunteers will also complete some brief surveys to assess state emotion, trait anger, and HAB. Volunteers will be asked to return between 24 and 96 hours later to complete another brief measure of HAB, state emotion, and a brief self-report survey about their online (public behavior only), driving, and other behaviors over the preceding 24 hours. We hypothesize that volunteers who receive the genuine training will display the less hostile bias and report lower anger and aggression in their daily behaviors when assessed at the second time-point.

If successful, these findings would provide evidence that HBMT is effective in affecting real-life behaviors and help convince potential stakeholders of the value of HBMT. Future research could validate effectiveness in operational units as well as with unhealthy populations (e.g., anger management groups). Future research could also test the effectiveness of HBMT on behavioral health outcomes for usage by clinicians and portable use by individuals with unhealthy hostile bias and problems with social aggression when isolated from traditional behavioral health care (e.g., far forward deployed units).

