## 8.5 Randomization and Volunteer Assignment

Volunteer assignment to each of the two experimental conditions is semi-randomized (i.e. random except that computer ensure equal sample sizes across experimental conditions). The randomized assigning of participants is done by the study web-page/program at volunteerscience.com. The computer program randomly assigned volunteers to one of the two conditions when they begin the study.

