## 8.7 Study Materials and Manipulations

### 8.7.1 HBMT

This is a training developed by the PI (see Appendix E), but based on the existing fragment lexical decision task (Neely et al., 1989) and Go/No-Go task (Fillmore et al., 2006). It was used and validated in a previous recent study (WRAIR #2574). This task is completed entirely on the computer. For this task, volunteers see incomplete word fragments (one at a time) that appear at the center of the computer screen. Most of the word fragments could be completed to form either aggressive or non-aggressive words (e.g., “K I \_ \_” could be completed as either an aggressive word, “KILL”, or a non-aggressive word “KISS”, “KILT”, etc.). Some of the fragments could only be completed to form non-aggressive words (e.g., HA \_ PY), and the remaining fragments could only form aggressive words (e.g., A \_ \_ ACK). Volunteers are instructed to respond to these cues as quickly and accurately as possible by typing a complete word that can be formed from the fragment. Volunteers are randomly assigned to either a real-training or a fake-training. Those in the real-training condition are told to try and complete each fragment to form a positive/non-aggressive word and to refrain from typing altogether if the fragment could *only* be completed as a negative/aggressive word. Participants are given 12 seconds to respond to each cue. Volunteers randomly assigned to the fake training will be told to complete the fragments with the first word that comes to mind. This fake training still exposes volunteers to the training stimuli and a computer task, but does not train inhibition or selectively prime non-hostility, which are the hypothesized mechanisms of the training. We do not believe there is a meaningful risk this task could unintentionally prime increased hostility given that prior research found no evidence of this, despite prior research including experimental conditions that were designed to use this this training to increase hostility (WRAIR # 2574). Actual responses in this task are not the primary outcome being measured. Rather, the HBMT is used to prime either hostile attribution bias or a reduction in hostile attribution bias and the key outcome measures are reported HAB, anger, and aggression.

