#### **10.6 Financial Incentives to Volunteers**

Volunteers will be paid up to \$5 for their participation in this study. All volunteers who complete time-point one of the study will receive \$3 and volunteers will receive an additional \$2 if they complete time-point two of the study. This rate is standard pay for MTurk work (See Hitlin, 2016). Most MTurk tasks pay 10 cents or less and result in less than an equivalent hourly wage of \$5. Volunteers will not be paid for participation in a time point if they do not complete an entire time point (i.e., progress through each activity/survey and reach the end screen; volunteers may skip any question they do not wish to answer on surveys without affecting payment). If a volunteer is terminated from the study as a result of website, server, or study program related failures (e.g., server goes down during study), they may request payment by contacting the PI directly. The PI will ask Volunteerscience.org to verify that the server/website failure had occurred and if so to pay the volunteer. The approval authority of such requests is the PI. Volunteerscience.com will track the performance of each volunteer using their MTurk handle and calculate compensation appropriately without sharing any PII (including MTurk handle) with ARL or WRAIR staff.

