### **11.4 Deviations from Protocol**

A log of all deviations from the protocol will be maintained by the study staff, and reported to WRAIR HSPB, as applicable. Actions taken in response to the deviation, and the impact of the deviation will be assessed by the PI (or AI assigned this duty) and recorded as significant or insignificant. As it is common for MTurk volunteers to quit an MTurk task prior to completion, self-withdrawals will not, on their own, be considered a deviation (unless associated with another deviation).

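### Eligibility does not exclude MTurk workers who already took part in the earlier HBMT study, WRAIR #2574

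*Combined protocol and SAP*

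**What the plan says.** **Who may enter.** Section 8.4.2 opens with "All volunteers must meet the following criteria to be included in the study" and lists only adult age and location in the United States or another mainly English-speaking country. Section 8.4.1 describes the only platform filter: "Prerequisites will be set to restrict participation to MTurk users who are located in the United States and/or other primarily English speaking countries". There is no exclusion list, and the advertisement in Appendix A sets no first-time condition.

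**Who has already met the task.** Section 8.1 says: "HBMT was specifically tested using an MTurk sample previously (WRAIR #2574) with large effect sizes observed". The Précis (Section 2) says that the real and placebo versions used here are those validated in WRAIR #2574. Sections 6.1 and 8.7.1 call that study recent, and Section 6.1 says its volunteers completed one session.

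**How arms are assigned.** Section 8.5 says: "The computer program randomly assigned volunteers to one of the two conditions when they begin the study". It has no rule for a volunteer who has seen the task before or who enters a second time.

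**Who holds the identifiers.** Under Section 8.6 the platform replaces MTurk IDs before any data reach the research staff. Section 10.6 has the platform follow each volunteer's performance, and work out payment, by MTurk handle.

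**The concern.** The trial compares people given the real training with people given a fake version that should not affect them. That contrast is cleanest when nobody has met either version before. As written, a worker who had the real training in WRAIR #2574 can be assigned to the fake arm, and one who had the fake version can be assigned to the real arm.

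Two things are at stake. First, a fake-arm volunteer who has already been trained may differ less from the real arm, which shrinks the observed effect. Second, the instructions in Appendix E differ visibly between versions: the real one asks for non-negative words and for no response to stems that can only be negative, while the fake one asks for any word. Someone who has seen one set can notice on meeting the other that versions exist, and may guess their purpose. The Section 3.4 endpoints, HAB and daily aggressive behaviour, are self-reported, as is state anger (Appendix H), so recognition can affect the answers.

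The research staff could not find these volunteers afterwards from MTurk IDs, because they never receive them. Any screen has to be in place before assignment.

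**Working it through.** **1. Can a WRAIR #2574 worker enter?** Both stated criteria concern the person's age and place. Taking part in WRAIR #2574 changes neither, and the recruitment route is the same. No other section supplies a bar. So the answer on the text is yes.

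**2. Is the exposure balanced?** It happened before this study's assignment, and assignment is random within a 1:1 constraint (Sections 3.3 and 8.5). The expected share of previously exposed volunteers is therefore the same in both arms at assignment. This route can weaken the contrast, but it does not by itself favour one arm.

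**3. Reproduce the planned sample size.** Inputs from Section 7.2: d = 0.4 (about half of 0.78), 80% power, 100 completers per arm. Alpha of 0.05 is from Section 9.2. Section 7.2 does not name the test, so I assume a comparison of two means on the SD = 1 scale.

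- Per arm, two-sided: n = 2 × (1.960 + 0.842)² / 0.4² = 98.1, rounded up to 99, or 198 in total. This agrees with the stated 200.
- Enrolment with 50% drop-out (Section 3.2): 200 / (1 − 0.5) = 400, as stated.
- Power at 100 per arm from the t-distribution: 80.4% two-sided and 88.0% one-sided. The stated 80% therefore matches a two-sided test. Section 9.2 specifies one-tailed tests for the directional hypotheses of Section 5.1, so both are shown below.

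**4. Illustrate the dilution.** Let f be the share of completers who contribute no real-versus-fake difference. The documents give no value for f; 5% and 10% are assumptions. Then d becomes 0.4 × (1 − f), and power comes from a two-sample t-test with noncentrality d × √(100/2).

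| f | d | noncentrality | two-sided power | one-sided power |
|---|---|---|---|---|
| 0 | 0.40 | 2.83 | 80.4% | 88.0% |
| 5% | 0.38 | 2.69 | 76.2% | 84.9% |
| 10% | 0.36 | 2.55 | 71.7% | 81.4% |

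The model is a worst case for each exposed person: it assumes that earlier exposure removes the whole difference.

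**The case against.** **Carry-over may be small.** The protocol itself expects training effects to fade. Section 5.2(a) predicts decline within 24 to 96 hours, and Section 7.2 cuts the planning effect partly because of that delay. One session in an earlier study may leave little behind, and a formerly exposed volunteer assigned to the real arm still receives the full training now. The size, date and worker overlap of WRAIR #2574 are not given. On the one-sided test, power stays above 80% even at f = 10%. All of this stands, and it is why the power figures are only an illustration. It does not answer the recognition point, since remembering a task need not fade as a priming effect does.

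**A condition may sit elsewhere.** The consent document (Appendix C) was not available for this check and could contain a first-time condition. If so, Section 8.4.2 should still carry it.

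**Two stronger readings that the documents do not support.**

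- *Arm-shopping.* A reader might combine three statements: assignment occurs on starting, "it is common for MTurk volunteers to quit an MTurk task prior to completion" (Section 11.4), and "Volunteers will not be paid for participation in a time point if they do not complete an entire time point" (Section 10.6). The inference would be that volunteers quit and restart until they get the version they prefer. No section says that re-entry triggers a new assignment. The platform tracks performance by handle as well as payment, invites time-one volunteers back (Section 3.3), and must link the two time-points for the change analyses in Section 9.1, so a per-worker record is implied. The advertisement mentions a single vocabulary task, and nothing shows which version volunteers would prefer. The documents are silent on re-entry, and silence is not a demonstrated fault.
- *Hostility carry-over.* Section 8.7.1 refers to "prior research including experimental conditions that were designed to use this this training to increase hostility", and a reader might fear that former volunteers from those conditions bring raised hostility into either arm. The same sentence reports that the earlier research found no evidence of such priming. That leaves no basis in the documents for the fear.

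**Conclusion.** The eligibility gap is real and follows directly from the text: Sections 8.4.1 and 8.4.2 admit WRAIR #2574 workers, who may then receive a different version of the same task. The expected consequence is some dilution and some loss of masking on self-reported outcomes. Systematic imbalance between arms is not expected from this route.

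The size is unknown. Under the assumed shares and the zero-contrast worst case, two-sided power falls by about 4 points (f = 5%) or 9 points (f = 10%), and one-sided power by about 3 or 7 points. Two-sided, the planned 200 completers leave almost no margin. One-sided, they leave some. The documents support no particular share, so these figures should not be read as a forecast.

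The change is worth making because it is cheap and must precede assignment.

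**What to change.** 1. **Section 8.4.2, new criterion (c):** no previous participation in WRAIR #2574. Apply it by having the platform block those worker IDs before the posting is shown. Whether the IDs were kept is not stated, and Section 8.11 says that this study will not keep its own. If they are unavailable, ask one screening question before assignment, describing the earlier word-fragment task, since volunteers would not know the study number.
2. **Section 8.5, one sentence as a safeguard:** each MTurk ID is assigned once, at time-point one, and keeps that arm on any re-entry and at time-point two. If the platform already works this way, the sentence only records it.

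Criterion (c) should not be widened to bar anyone with an earlier session of this study. Read literally, that would exclude every volunteer at time-point two and contradict item 2.

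**Cost:** two sentences and a platform setting, or one extra question. IDs can stay with the platform, so no identifying information need reach the research staff. The recruitment pool becomes slightly smaller, and the screen depends on self-report if the earlier IDs no longer exist.
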